7.2 Statistical Analysis

Effects of treatment will be compared using Intent-to-Treat principles using ANCOVA with BMI, gender and baseline fasting C4 as covariates. In order to reach 30 subjects, accrual will be set at 36 to replace any volunteer(s) who withdraw prior to taking less than 1 day of dosing. Any Subject who receives more than 1

day of dosing will be consider completed using the Intent-to-Treat analysis.

Primary endpoints are change in fasting serum C4 levels from baseline to Day 28 and change in stool consistency based on Bristol Stool Form Scale, BSFS from baseline to Day 28.

Secondary endpoints are

- Absolute change in stool consistency from baseline to Day 14 and Day 28 of treatment
- Average daily stool consistency score at Day 14 and Day 28 of treatment
- Maximum abdominal pain score rated by patient using an 11-point scale, 0 to 10 inclusive with 0 as none and 10 as worst imaginable pain
- Absolute change in abdominal pain from baseline to Day 14 and Day 28 of treatment
- Number of bowel movements per week
- Change in total fecal bile acid concentration between baseline and Day 28
- Proportion of fecal secretory (CDCA+ DCA) bile acid as measured in a single, random stool sample by a validated laboratory assay.
- Proportion of fecal primary (CDCA + CA) bile acid as measured in a single, random stool sample by a validated laboratory assay.
- Total fecal bile acid concentration in a single, random stool sample as measured by a validated laboratory assay.
- Total aldafermin concentration in serum as measured by a validated laboratory assay

Adverse events (AEs) will be listed and summarized by system organ class and preferred term, as well as according to severity and causality/relationship to study treatment.

Observed values for clinical laboratory tests, vital signs and safety 12-lead ECGs will be summarized by treatment. Observed values will be classified as normal, abnormality that is not clinically significant, and clinically significant abnormality by treatment.

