2.2 Study Endpoints

Primary Endpoints

1. Change in fasting serum C4 levels from Baseline to Day 28
2. Change in stool consistency based on the Bristol Stool Form Scale, BSFS from Baseline to Day 28

Secondary Endpoints

1. Stool consistency based on Bristol Stool Form Scale, BSFS
 - a. Absolute change in stool consistency from baseline to Day 14 and Day 28 of treatment.
 - b. Average daily stool consistency score at Day 14 and Day 28 of treatment

[figure not shown]
2. Maximum abdominal pain score rated by patient using an 11-point scale, 0 to 10 inclusive with 0 as none and 10 as worst imaginable abdominal pain.
3. Absolute change in abdominal pain from baseline to Day 14 and Day 28 of treatment.
4. Number of bowel movements per week
5. Change in total fecal bile acid concentration between baseline and Day 28.
6. Proportion of fecal secretory (CDCA + DCA) bile acid as measured in a single, random stool sample by a validated laboratory assay.
7. Proportion of fecal primary (CDCA + CA) bile acid as measured in a single, random stool sample by a validated laboratory assay.
8. Total fecal bile acid concentration in a single, random stool sample as measured by a validated laboratory assay.
9. Total aldafermin concentration in serum as measured by a validated laboratory assay

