3.2 Visit 1 Screen

The patient will fast for 12 hours and avoidance of alcohol for 24 hours before the visit if they wish to have their screening safety bloods drawn. The patient and a study team member will review the informed consent. Adequate time for questions and discussion will be allowed. The patient will be given a signed hard copy of the informed consent and a copy will be placed in the patient's electronic medical history. A study physician will review the study's eligibility criteria, the patient's medical history and perform a physical examination. Height, weight and vital signs (pulse, blood pressure, respiration rate and temperature) will be obtained. If the patient does not have a prior laboratory assessment to confirm the presence of BAM/BAD (20-22), a small volume blood sample will be drawn to test for serum C4. Blood and urine will be obtained for routine safety labs of hematology, chemistry, lipid panel and a dipstick urinalysis. A 12-lead electrocardiogram (ECG) will be performed. The patient will complete three standard questionnaires, the Short Bowel Disease questionnaire (short BDQ), the Hospital and Anxiety Depression questionnaire and the Quality-of-Life questionnaire; these questionnaires are included in the protocol appendices. The patient will be given a bowel pattern diary to record in for at least 7 days prior to Visit 2; the diary page is included in the protocol appendices. The patient will be given a stool kit to collect a single, random stool sample to bring in at Visit 3.

If a patient elects to withdraw from taking some prohibited medications, a 14-day washout will be required after which the patient may proceed with laboratory tests, bowel pattern diary and stool collection.

Visit 1 activities may be combined with Visit 2 for greater convenience if the patient has not taken any of the prohibited medications within 2 weeks.

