6.8 Assessment of Abdominal Pain, Stool Frequency and Consistency

Patients will complete a daily bowel pattern diary throughout the study to record and assess their most severe abdominal pain on an 11-point scale and timing of each bowel movement, consistency based on Bristol stool form scale, ease of passage, and sense of completeness of evacuation. Ease of stool passage was also assessed based on a 7-point scale (1: manual disimpaction; 2: enema needed; 3: straining needed; 4: normal; 5: urgent w/o pain; 6: urgent w/pain; 7: incontinent). The Bristol stool scale and a sample diary page are included in the protocol appendices.

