7. STATISTICAL CONSIDERATIONS

7.1 Sample Size and Statistical Power

Based on the endpoints of interest in patients with bile acid diarrhea [12], the proposed sample sizes have ~80% power (2-sided $\alpha=0.05$) to detect clinically relevant effect sizes in serum C4 and stool form (expressed as detectable difference $[\Delta]$ in 2 groups:

Table 1: Detectable differences based on 80% power in patients with BAD *not* receiving BA sequestrant

Response	Mean (SD)	Detectable Δ absolute with n=9 per group
Serum C4 ng/mL	72.3 (45.6)	64.1 (1.34*SD or 89 % of baseline mean)
% fecal primary BA	15.7 (20)	28.1 (1.79*SD or 179 % of baseline mean)
# BMs per week	15.1 (7.1)	10.0 (1.41*SD or 66 % of baseline mean)
Stool form (BSFS 1-7 scale)	4.4 (1.12)	1.58 (1.41*SD or 35.9 % of baseline mean)

Based on our previous open-label study demonstrating effects of a bile acid sequestrant (colesevelam) as a typical baseline results for patients on bile acid sequestrants:

Table 2: Detectable differences based on 80% power in patients with BAD receiving BA sequestrant

Response	Mean (SD)	Detectable Δ absolute with n=6 per group
Serum C4 ng/mL	112.5 (50.6)	90.8 (1.79*SD or 80.7 % of baseline mean)
% fecal primary BA	2.7 (7.4)	13.3 (1.80*SD or 492% of baseline mean)
# BMs per week	21.7 (7.1)	12.75 (1.80*SD or 58.8 % of baseline mean)
Stool form (BSFS 1-7 scale)	4.6 (0.6)	1.08 (1.80*SD or 23.5% of baseline mean)

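### The primary analysis of change in stool consistency adjusts for baseline C4 but not for baseline BSFS, which usually gives up some precision

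*Combined protocol and SAP*

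**What the plan says.** The model is stated in two places, Section 7.2 and the Statistical Methods entry of the synopsis, with the same covariates: "ANCOVA with BMI, gender and baseline fasting C4 as covariates". In both it covers treatment effects in general. Section 7.2 then names two primary endpoints. The first concerns C4 at Day 28 relative to its pre-treatment value. The second, as Section 2.2 lists it, is "Change in stool consistency based on the Bristol Stool Form Scale, BSFS from Baseline to Day 28". Nothing in the documents adds baseline BSFS for the second endpoint, or says that the baseline covariate changes with the endpoint.

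Baseline BSFS is collected. The daily diary in Section 6.8 records the "timing of each bowel movement, consistency based on Bristol stool form scale". Section 3.2 gives the patient the diary "to record in for at least 7 days prior to Visit 2", and under Section 3.4 it is handed back at Visit 3. The endpoint is a change score, so the baseline value is needed in any case.

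Section 7.1 gives detectable BSFS differences at 80% power: "1.58 (1.41*SD or 35.9 % of baseline mean") off sequestrant with 9 per group, and "1.08 (1.80*SD or 23.5% of baseline mean") on sequestrant with 6 per group.

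**The concern.** A change score analysed without its own baseline fixes the slope of Day 28 on baseline at 1. If the true slope differs, as it does when patients regress toward the mean, part of the baseline variation stays in the residual. Adding the baseline as a covariate removes it. Here the C4 endpoint gets that benefit and the stool endpoint does not.

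The stake is the width of the confidence interval for a primary endpoint with 15 patients per arm, and power if the true effect is smaller than planned. A smaller effect is plausible on the protocol's own evidence: Section 1.2 describes a four-week randomized trial of colesevelam with clear biomarker changes and no significant effect on stool frequency or consistency.

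**Working it through.** **1. Reproduce the plan's figures.** Two-sample t-test, two-sided 0.05, 80% power: the detectable standardized difference is 1.407 SD with 9 per group and 1.796 SD with 6. Then 1.407 × 1.12 = 1.58 and 1.796 × 0.6 = 1.08, as in Tables 1 and 2. These are unadjusted comparisons within each sequestrant stratum and use no baseline to Day 28 correlation.

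**2. Inputs for the pooled ANCOVA.** From the documents: 15 per arm (9 off and 6 on sequestrant) and BSFS SDs of 1.12 and 0.6, read as baseline SDs. The pooled within-stratum SD is √[(9 × 1.12² + 6 × 0.6²)/15] = 0.947. Assumed, because the documents give neither: rho, and k = Day 28 SD divided by baseline SD.

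**3. Variance ratio, as written against with baseline BSFS.** In units of the baseline variance:
- change score without own baseline: 1 + k² − 2·rho·k
- with own baseline: k²(1 − rho²)

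The first exceeds the second by (1 − rho·k)², so in large samples adjustment never loses. In a small trial each estimated covariate has a price. With N = 30 and q covariates, the variance is inflated by about (N − 3)/(N − 3 − q), which is 27/24 for three covariates and 27/23 for four. The large-sample ratio is therefore multiplied by 23/24.

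Two examples:
- k = 1, rho 0.3: 1.4/0.91 = 1.538; × 23/24 = 1.47.
- k = 1.25, rho 0.7: 0.8125/0.7969 = 1.020; × 23/24 = 0.98.

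| Baseline C4 unrelated to BSFS | rho 0.3 | 0.5 | 0.7 | 0.85 |
|---|---|---|---|---|
| k = 0.8 | 1.91 | 1.68 | 1.53 | 1.51 |
| k = 1 | 1.47 | 1.28 | 1.13 | 1.04 |
| k = 1.25 | 1.22 | 1.07 | 0.98 | 0.97 |

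Simulation of the two actual models (9 off and 6 on sequestrant per arm, means and SDs from Tables 1 and 2, normal data; BMI and gender assumed unrelated to outcome) agrees. At k = 1 it gives 1.49, 1.29, 1.14 and 1.05.

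**4. C4 as a partial proxy.** If baseline C4 and baseline BSFS correlate at 0.6 (assumed), and C4 relates to Day 28 BSFS only through baseline BSFS, the simulated ratios at k = 1 are 1.32, 1.18, 1.08 and 1.02.

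**5. Precision at k = 1, C4 unrelated, rho 0.3, 0.5, 0.7.**
- SE as written: 0.43, 0.37, 0.28 points. With baseline BSFS: 0.36, 0.32, 0.26.
- 95% CI half-width: 0.89, 0.75, 0.58 against 0.73, 0.66, 0.55.
- Equivalent size, 15/ratio: 15/1.49 = 10.1, 15/1.29 = 11.6 and 15/1.14 = 13.2 per arm.

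**6. Power at the Section 7.1 differences.** The average effect is (9 × 1.58 + 6 × 1.08)/15 = 1.38 points.
- k = 1, rho 0.3, 0.5, 0.7: 86%, 95%, >99% as written; 95%, 98%, >99% with baseline BSFS.
- k = 1.25, rho 0.3: the SE as written is 0.947 × √1.8125 × √(2/15) × √(27/24) = 0.49, and power is about 77%, against 84% with baseline BSFS.
- Illustration only, effect 1.08 in both strata, k = 1: 68%, 81%, 95% against 83%, 89%, 97%. Section 7.1 does not state this effect for the off-sequestrant stratum.

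**7. Validity.** With no treatment effect and k = 1, both models rejected in 4.7 to 5.0% of simulated trials, and the mean estimate was within 0.003 of zero.

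**The case against.** The strongest objection is that the gain is not guaranteed. It depends on how far the slope rho·k is from 1. The documents give neither rho nor a Day 28 SD, and equal SDs are as much an assumption as unequal ones. With a Day 28 SD 25% larger than baseline and rho at 0.7 or above, adding baseline BSFS buys nothing and costs up to about 3% of variance. This stands, and the size of the loss has to be stated conditionally. It does not reverse the recommendation: the cost is limited to estimating one more coefficient, while the gain elsewhere in the range is several times larger.

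A second objection is that the plan is already valid and prespecified, so this is only a matter of efficiency. That also stands and sets the weight of the point.

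A reader might go further and infer that the stool analysis is biased or its type I error inflated. It is not: treatment is randomized, and a change score compared between arms estimates the same effect with or without its baseline in the model.

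**Conclusion.** The omission is in the text of both places where the model is given, and the covariate is available. The consequence is usually a loss of precision on one of the two primary endpoints. With equal SDs the variance is about 1.5, 1.3, 1.1 and 1.05 times what it could be at rho 0.3, 0.5, 0.7 and 0.85; a strong C4 proxy reduces this to about 1.3, 1.2, 1.1 and 1.0. A smaller Day 28 SD makes the loss larger, and a larger one can remove it.

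Two inferences about power go too far in opposite directions. One is that the omission makes the stated 80% unattainable: with equal SDs the pooled analysis as written has about 86% or more at the Section 7.1 differences. The other is that 80% is therefore safe: with a Day 28 SD 25% larger and rho 0.3 it falls to about 77%. The documents settle neither, because Section 7.1 gives one SD per stratum and no correlation.

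The check covers the change in BSFS only and does not support a rule for every other endpoint. This is a cheap improvement, not a flaw that invalidates the analysis.

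**What to change.** In Section 7.2 and the synopsis, state before unblinding: *The change in stool consistency from baseline to Day 28 is analysed by ANCOVA with the baseline diary-mean BSFS, from the pre-treatment diary, in addition to BMI, gender and baseline fasting C4.* The C4 analysis does not change.

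The cost is one residual degree of freedom (25 to 24) and a stated baseline window. The window needs its own line, because Section 3.1.1 ties the seven or more diary days to Visit 3 while Section 3.2 ties them to Visit 2. No new data or patients are needed. Fixing the covariate before unblinding matters, since adding it later could look driven by the results.

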Statistical Methods	
Sample size: 30 patients, 15 in placebo group, 15 in aldafermin treatment group.
 
Statistical analyses: Effects of treatment will be compared using Intent-to-Treat principles using ANCOVA with BMI, gender and baseline fasting C4 as covariates. Adverse events (AEs) will be listed and summarized by system organ class and preferred term, as well as according to severity and causality/relationship to study treatment. Observed values for clinical laboratory tests, vital signs and safety 12-lead ECGs will be summarized by treatment. Observed values will be classified as normal, abnormality that is not clinically significant, and clinically significant abnormality by treatment. Results of other safety assessments will be listed and summarized as appropriate.
 
Statistical power: Based on the prior open-label study, the proposed sample size of 15 per group has ~80% power (2-sided $\alpha=0.05$) to detect clinically relevant effect sizes in serum C4 and stool consistency.
 
Anticipated results and significance: Aldafermin will reduce serum C4 and percent

[figure not shown]
	fecal primary bile acids in a random stool sample; preliminary data will be obtained regarding efficacy on stool frequency and stool consistency in BAM/BAD with high BA excretion.
--	---

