4. STUDY POPULATION

4.1 Number of Patients

Approximately 36 patients with BAM/BAD irritable bowel syndrome-diarrhea will be enrolled.

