5.5. Randomization

Patients who complete screening assessments and meet all eligibility criteria will be assigned a unique randomization identification number at the time of study treatment administration. Once a randomization number has been allocated to a subject, it may not be assigned to another patient.

DESIGN: Randomized placebo-control trial based using **BLOCK RANDOMIZATION** so that equal numbers of patients are randomized to placebo and aldafermin 1 mg in two blocks:

- a. Patients OFF bile acid sequestrants**
- b. Patients ON bile acid sequestrants.**

Randomized treatment assignment will be considered blinded as per the following: The randomization assignments will be available to the study pharmacy staff that is preparing the study treatment, who will not be involved in any other aspect of the study including administration of the study treatment. Randomization assignments will not be made available to the patients or study staff responsible for the monitoring and evaluation of safety assessments.

In the absence of a medical emergency, the blinded randomization for this study will not be revealed to the Principal Investigator and study team until all data are entered in the database, edit checks are performed, queries closed, and the database is officially locked.

Breaking the blind is expressly forbidden except in the event of a medical emergency where the identity of the study treatment must be known in order to properly treat the patient. In the event of a medical emergency, it is requested that the investigator contact the sponsor prior to breaking the blind. If breaking the blind is required because of a medical emergency, the treatment identity would be revealed by the investigator or designee, for that patient only. Reasons for treatment unblinding must be clearly explained and documented.

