8.4 Safety Review Plan

Study progress and safety will be reviewed quarterly (and more frequently, if needed). Progress reports including patient recruitment, retention/attrition, and AEs will be provided to the Independent Monitor every year. An annual report will be compiled and will include a list and summarization of AEs. In addition, the annual report will address:

1. Whether AE rates are consistent with pre-study assumptions;
2. Reason for dropouts from the study;
3. Whether all participants met entry criteria;
4. Whether continuation of the study is justified on the basis that additional data are needed to accomplish the stated aims of the study; and
5. Conditions whereby the study might be terminated prematurely (i.e., voluntary dropout of > 40% of cohort).

The annual report will be reviewed by the independent monitor and will be forwarded to the IRB on an annual basis.

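### The six extra places (36 accrued for 30) cover only withdrawal around first dosing, so the ~80% power for 15 per group assumes Day 28 data on every dosed patient; an assumed 10% post-dose loss would leave about 75%

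*Combined protocol and SAP*

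**What the plan says.** The synopsis (Statistical Methods) sets the sample at "30 patients, 15 in placebo group, 15 in aldafermin treatment group" and states that "the proposed sample size of 15 per group has ~80% power". It gives no detectable difference for that statement. Section 7.1 gives detectable differences only by stratum: n=9 per group off sequestrant (Table 1) and n=6 per group on sequestrant (Table 2). These add to 15 per group.

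Section 7.2 explains the accrual margin: "accrual will be set at 36 to replace any volunteer(s) who withdraw prior to taking less than 1 day of dosing". It then says that a subject with more than one "day of dosing will be consider completed using the Intent-to-Treat analysis". The primary endpoints in sections 2.2 and 7.2 are the changes from baseline to Day 28 in fasting C4 and in stool consistency.

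Three other places bear on the point:

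- Section 5.5: eligible patients "will be assigned a unique randomization identification number at the time of study treatment administration".
- Section 4.1, and the synopsis in similar terms: "Approximately 36 patients with BAM/BAD irritable bowel syndrome-diarrhea will be enrolled", with no mention of a reserve.
- Section 4.4: its title refers to replacement. Its text lists reasons for leaving the study but contains no replacement rule.

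**The concern.** The margin guards against a loss that hardly touches the analysed sample. Because randomization numbers are given at treatment administration, most people who leave before dosing were never randomized and never belonged to the 30. A patient lost on Day 3 does fill one of the 30 places, has no Day 28 value, and under section 7.2 is not backed up.

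Calling such a patient completed does not create a Day 28 measurement, and no section says how a missing one is to be handled. The 30 in the power statement are therefore 30 dosed patients, while an ANCOVA on change to Day 28 needs 30 patients with Day 28 data. In a trial of this size each missing value costs noticeable power.

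**Working it through.** **Inputs.** From the plan: two-sided alpha 0.05; 1:1 allocation; 15 per group; Table 1 (n=9) C4 64.1 with SD 45.6 and stool form 1.58 with SD 1.12; Table 2 (n=6) C4 90.8 with SD 50.6 and stool form 1.08 with SD 0.6. Assumed, because the plan gives none: the post-dose loss, taken as 10% to 20%.

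**Formula.** Two-sample t-test with n per group and standardized effect d: noncentrality d × √(n/2), degrees of freedom 2n − 2, power from the noncentral t distribution.

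**Step 1: reproduce the plan's figures with no loss.**

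| Table | Endpoint | d | n per group | Power |
|---|---|---|---|---|
| 1 | C4 | 64.1/45.6 = 1.41 | 9 | 79.9% |
| 1 | Stool form | 1.58/1.12 = 1.41 | 9 | 80.2% |
| 2 | C4 | 90.8/50.6 = 1.79 | 6 | 80.0% |
| 2 | Stool form | 1.08/0.6 = 1.80 | 6 | 80.2% |

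The tables reproduce at 80% with every patient analysed. The power basis holds no allowance for attrition.

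**Step 2: infer the effect behind the 15-per-group claim.** Solving for 80% power at n=15 gives d = 1.060. Taking off 3 degrees of freedom for covariates gives 1.064, and the normal approximation gives 1.023.

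**Step 3: apply post-dose loss, holding each effect at its 80% value.**

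| Loss | n=15, d=1.060 | n=9, d=1.407 | n=6, d=1.796 |
|---|---|---|---|
| 0% | 80.0% | 80.0% | 80.0% |
| 10% | 75.4% (13.5 per group) | 75.1% (8.1) | 74.5% (5.4) |
| 20% | 69.9% (12 per group) | 69.1% (7.2) | 67.8% (4.8) |

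At 15 per group and 10% loss the other variants give 75.3% (13 against 14 patients), 75.2% to 75.3% (covariate degrees of freedom), 75.7% (normal approximation) and 75.1% (random binomial loss). The shortfall is 4.3 to 4.9 points.

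**Step 4: pooled comparison at the larger tabulated effect.** With d = 1.41, 15 per group has 96% power, 94% after 10% loss and 91% after 20%.

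**Step 5: what 36 places could cover.** Keeping 30 evaluable at 10% loss takes 30/0.9 = 33.3, so 34 dosed patients (17 per group). With all 36 dosed, 36 × (1 − 1/6) = 30, so the ceiling holds 80% up to a loss of one sixth. At 20% loss, 36 × 0.8 = 28.8, or 14.4 per group, and power at d = 1.060 is about 78%.

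**The case against.** - **The 1.06 SD effect is not in the documents.** True. It is the effect implied by 80% at 15 per group. If the true effect is as large as the tabulated ones, the pooled comparison has ample reserve (step 4). A reader might infer that the trial is underpowered overall; the documents do not support that. What stands is that the stated claim has no allowance for loss, and neither do the stratum figures. Section 7.2 specifies no within-stratum test, however.
- **The dropout rate is an assumption.** Also true. A reader might take "voluntary dropout of > 40% of cohort" in section 8.4 as a tolerated or expected rate. It is only an example of a condition under which the study might be stopped early. The list in section 4.4 likewise names possible reasons for leaving, not an expected frequency.
- **The ANCOVA may not be complete-case.** Section 7.2 does not say that patients without a Day 28 value are dropped. It does not say how they would be included either, so the loss figures are conditional on dropping them.
- **All 36 might be dosed.** Section 4.1 and the synopsis can be read that way, and 10% loss would then leave 16.2 per group and 83% power. Section 7.2 is the more specific text and ties the extra six to early withdrawal. Its wording is garbled and leaves exactly one day of dosing undefined, so the places need reconciling.
- **Covariates may recover power.** Adjusting for baseline C4 could help the C4 endpoint if the correlation is strong. No baseline stool covariate is listed, so this does not clearly help stool form.

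**Conclusion.** The point holds in a limited form. The accrual margin is assigned to withdrawal around or before the first day of dosing, and the ~80% power for 15 per group assumes Day 28 data on all 30 dosed patients. Under an assumed 10% post-dose loss the claim falls to about 75%, which is 4 to 5 points short; under 20% it falls to about 70%. It would be too strong to say that 10% loss costs five points or more at 15 per group: that needs about 10.7% loss with the t-test.

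The size rests on three assumptions: the true effect is the one that gives exactly 80% at 15 per group, the loss rate is as assumed, and patients without a Day 28 value drop out of the analysis. It is a worthwhile and cheap correction to the plan, not a fatal flaw.

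**What to change.** 1. In section 7.2, within the existing ceiling of 36, continue randomizing until 30 patients have Day 28 C4 and stool data, with completeness judged blind to treatment. Keep every randomized patient in the ITT analysis; later patients are added and do not replace anyone. Reconcile section 4.1 and the synopsis with this rule, and define the status of exactly one day of dosing.
2. Analyse Day 14 and Day 28 jointly in a repeated-measures mixed model with the Day 28 contrast as primary. C4 is drawn and the diary returned at Visit 4, so a patient lost after that visit still contributes data already collected.
3. Restate the power as about 80% for 15 evaluable per group, name the detectable difference, and add that it is about 70% to 75% if 10% to 20% of 30 dosed patients lack Day 28 data.

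**Cost.** Protocol and SAP wording and slightly more modelling work. Nobody is added beyond the 36 already planned, but up to six more of them may be dosed. Places used by withdrawals before dosing reduce what is left for later loss if both count against the same 36, and above a loss of one sixth the ceiling no longer secures 30 evaluable patients.
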